c. **Please summarize any protocol deviations/violations or unanticipated problems (UPs)/adverse events (AEs) since the last continuing review or original approval (if this is your first continuing review). Please indicate if any of the unanticipated problems/events are being reported to the IRB for the first time. If you have or will make changes to your protocol as a result of any unanticipated problem/event or adverse event, please summarize those changes in Question #5 below.**

Please see AE log. No deviation occurred since the last approval period.

e. **Complaints about the research during the last year.**

none

3. **A summary of any recent findings, literature, or other relevant information (especially pertaining to risks), if applicable.**

none

4. **Description of the remainder of project:**

N Do you plan to recruit more subjects?

Y If "No," have all subjects completed all research-related interventions? Note: Protocols must be renewed to continue recruiting participants and/or collect data from already recruited participants.

Y Are you only performing data analysis? NOTE: If you are analyzing data with no identifiers (i.e., you cannot link your data to individuals), you can close your protocol by submitting a Final Report.

N Does this protocol have a Data Safety Monitoring Board (DSMB)?

If you do have a DSMB, have reports been submitted to the IRB and/or the Sponsor? Upload any DSMB reports that have not yet been submitted to the IRB since the approval or last continuing review.

5. **Summarize all approved changes in the protocol since the last continuing review or since the original approval (if this is your first continuing review). For example: Have you amended your protocol during the past year? Are you requesting to make any changes for the upcoming year? Have you**

Protocol Title: Does Dapagliflozin Augment The Favorable Adaptation To Endurance Exercise Training?
 Clinical Research Protocol Title: Dapagliflozin Augments The Favorable Adaptation To Endurance Exercise Training

Protocol Type: Biomedical

Date Submitted: 11/01/2018

Approval Period: 11/06/2018-11/05/2019

Important Note: This Print View may not reflect all comments and contingencies for approval. Please check the comments section of the online protocol. Questions that appear to not have been answered may not have been required for this submission. Please see the system application for more details.

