*** Purpose, Study Procedures, Background ***

Original Protocol Number (e.g., 07-226H)

Title (Please indicate if the protocol title is different from the proposal title)

Does Dapagliflozin Augment The Favorable Adaptation To Endurance Exercise Training?
Clinical Research Protocol Title: Dapagliflozin Augments The Favorable Adaptation To Endurance Exercise Training

Complete Sections 1 - 16. Specify N/A as appropriate. Do not leave any required sections blank.

1. Purpose of the study

a) Provide a brief lay summary of the project in <200 words. The lay summary should be readily understandable to the general public, and is, for example, what would be released to a newspaper if requested.

Exercise is frequently prescribed as a favorable lifestyle intervention to prevent/reverse type 2 diabetes. It is also prescribed in addition to concurrent pharmacological treatment, such as metformin. Recent data (animal and human) suggest that metformin may attenuate the favorable benefits of exercise training. In light of the physiological mechanism of Dapagliflozin (sodium-glucose co-transporter 2 (SGLT2) inhibition), one might speculate that rather than inhibit, it will augment the favorable adaptations to exercise training.

b) **What does the Investigator(s) hope to learn from the study?**

We wish to learn if Dapagliflozin augments the favorable adaptation to endurance exercise training in previously sedentary overweight/obese adult humans.

c) **Proposed Start Date (may not precede IRB approval date):**

On receipt of IRB approval (and FDA approval of IND application).

2.

Protocol Title: Does Dapagliflozin Augment The Favorable Adaptation To Endurance Exercise Training?
Clinical Research Protocol Title: Dapagliflozin Augments The Favorable Adaptation To Endurance Exercise Training

Protocol Type: Biomedical

Date Submitted: 11/01/2018

Approval Period: 11/06/2018-11/05/2019

Important Note: This Print View may not reflect all comments and contingencies for approval. Please check the comments section of the online protocol.
Questions that appear to not have been answered may not have been required for this submission.
Please see the system application for more details.

Study Procedures (If this is a student project, the methods section of the thesis or dissertation proposal must be attached in section #16 - Attachment section.)

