a) In lay language, describe all the procedures, from screening through end-of-study, that the human subject must undergo in the research project, including study visits, drug treatments, randomization and the procedures that are part of standard of care. Please note: Do NOT respond "See Attachment Section." If you would like to add tables, charts, etc., attach those files in the Attachment section (#16).

OVERVIEW

This is a randomized, placebo-controlled, double blind, repeated measures study. 30 sedentary adults will be recruited for participation and randomly assigned to one of two 12-week treatments: 1) supervised endurance exercise training 4 days per week plus daily oral administration of Dapagliflozin; 2) supervised endurance exercise training 4 days per week plus daily oral administration of placebo. Prior to and following completion of the treatment the following dependent variables will be quantified: a) maximal aerobic capacity; b) substrate utilization during standardized low-moderate intensity exercise; c) skeletal muscle aerobic enzyme activity; d) body composition; and, e) oral glucose tolerance, fasting glucose and insulin resistance.

Study participants will report to the Human Performance/Clinical Research Laboratory (HPCRL) on 51 separate occasions:

Visit 1: study participants will undergo screening: medical history, 12-lead electrocardiogram and blood pressure assessment at rest and during incremental exercise to volitional exhaustion, blood sampling, and measurement of body composition.

Visit 2: maximal oxygen uptake will be measured.

Visit 3: the metabolic response to standardized exercise will be determined.

Visit 4: an oral glucose tolerance test will be performed, and then skeletal muscle will be sampled.

Visits 5-48: 12 weeks of supervised exercise training. Concurrent with these visits, research participants will ingest, on a daily basis, either Dapagliflozin or placebo.

Visit 49: maximal oxygen uptake and body composition will be measured.

Visit 50: the metabolic response to standardized exercise will be determined.

Visit 51: an oral glucose tolerance test will be performed, and then skeletal muscle will be sampled.

DETAILED DESCRIPTION OF STUDY PROCEDURES

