Blood sampling – Blood (~ 20 ml) will be sampled from an antecubital or hand vein for subsequent analysis of circulating factors pertinent to inclusion/exclusion criteria, including glucose, aspartate aminotransferase, alanine aminotransferase, and total bilirubin. These blood analyses will be performed in on-site (Piccolo Xpress, Abaxis, Union City, CA). Testing for Hepatitis B/C will be performed at a local, external clinical lab (e.g. University of Colorado-Health North). Per the Medical Monitor's discretion follow up blood draws maybe requested.

Visit 2: Maximal oxygen uptake will be measured.

This procedures is standard for our lab and is currently active in other IRB-approved protocols (e.g. 12-3767H, 08-611H, 14-4756H, 13-4282H).

Maximal oxygen uptake - Oxygen consumption, carbon dioxide production and ventilation will be determined by indirect calorimetry during incremental stationary cycle ergometer exercise until volitional fatigue.

Visit 3: The metabolic response to standardized exercise will be determined.

This procedures is standard for our lab and is currently active in other IRB-approved protocols (e.g. 13-4282H, 13-4234H).

Subjects will perform stationary cycle ergometer exercise. Participants will exercise for 3 consecutive 10-minute periods at an external work rate of 25, 50 and 100 Watts. Respiratory exchange ratio, heart rate, and blood pressure will be recorded during the final 2-minutes of each 10-minute period. During the final 60-seconds of each 10-minute period, ratings of perceived exertion will be recorded. During the final 30-seconds of each 10-minute period, venous blood will be sampled for subsequent determination of circulating concentrations of glucose, lactate, non-esterified fatty acids, glycerol, and insulin.

Visit 4: An oral glucose tolerance test will be performed, followed by muscle sampling.

These procedures are standard for our lab. Each of the procedures is currently active in other IRB-approved protocols (e.g. 14-5201H, 13-4282H, 13-4366H).

Participants will report to the laboratory early in the morning, following a 12-hour fast and 24-hour

Protocol Title: Does Dapagliflozin Augment The Favorable Adaptation To Endurance Exercise Training?
Clinical Research Protocol Title: Dapagliflozin Augments The Favorable Adaptation To Endurance Exercise Training

Protocol Type: Biomedical

Date Submitted: 11/01/2018

Approval Period: 11/06/2018-11/05/2019

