Important Note: This Print View may not reflect all comments and contingencies for approval. Please check the comments section of the online protocol. Questions that appear to not have been answered may not have been required for this submission. Please see the system application for more details.

abstention from exercise. An intravenous catheter will be inserted into an antecubital or hand vein and kept patent with a saline drip. Following baseline blood sampling for fasting glucose and insulin, participants will ingest 75 g of dextrose dissolved in 250 ml of water over 10-minutes. Venous blood (~ 9 ml) will be sampled at time 0 (baseline) and 5, 10, 15, 20, 30, 45, 60, 75, 90 105 and 120 minutes for determination of concentration of blood glucose and insulin (commercially available assay).

On completion of the oral glucose tolerance test, skeletal muscle (~ 200 mg of vastus lateralis) will be sampled using standard techniques (Bergström needle) and analyzed for protein content and maximal enzymatic activities.

Visits 5-48: 12 weeks of supervised exercise training. Concurrent with these visits, research participants will ingest, on a daily basis, either Dapagliflozin or placebo.

All participants will complete a 12-week program of supervised exercise training. Exercise will begin with 3 training sessions per week of 20-40 minutes, and progress after 4 weeks to 4 sessions per week of 40-60 minutes. Participants will report their rate of perceived exertion (RPE); the target will be 13-to-15 (somewhat hard to hard). If an RPE indicative of moderate-to-heavy exercise is not achieved by a heart rate equivalent to 70-80% of heart rate reserve, the external work rate will be adjusted to achieve an appropriate training stimulus. Subjects will not be permitted to exercise within 5 beats per minute of their maximum heart rate. The exercise modalities will be treadmill walking/running, stationary cycle ergometer exercise, and elliptical ergometer exercise. The modalities will be varied between (but not within) sessions to avoid boredom and potential overuse injuries. In total, each participant will be scheduled to complete 44 exercise sessions. Every session will begin and end with a 5-minute self-paced warm-up/cool-down. These 5-minute periods will not be included in the training duration (for example, a 20 minute session will consist of a 5 minute warm-up, 20 minutes of exercise training, and 5 minutes of cool-down).

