*** Subject Population (a-g) ***

8.

Subject Population - In the space below, please detail the participants that you are requesting to recruit (include requested participant number and description of each group requested). (Input N/A if not applicable)

a) **Requested Participant Description (Include number of participants that you plan to study and description of each group requested, if applicable).**

We plan on enrolling 60 participants with estimation that 50% will screen out or not complete the study. We plan to complete the study in 30 overweight/obese adult volunteers (men and women).

b) **What is the rationale for studying the requested group(s) of participants?**

Adults who are overweight/obese are at the greatest risk of developing type 2 diabetes, thus overweight/obese adults potentially have the most to gain should the outcome of the study prove

Protocol Title: Does Dapagliflozin Augment The Favorable Adaptation To Endurance Exercise Training?
Clinical Research Protocol Title: Dapagliflozin Augments The Favorable Adaptation To Endurance Exercise Training

Protocol Type: Biomedical

Date Submitted: 11/01/2018

Approval Period: 11/06/2018-11/05/2019

Important Note: This Print View may not reflect all comments and contingencies for approval. Please check the comments section of the online protocol. Questions that appear to not have been answered may not have been required for this submission. Please see the system application for more details.

favorable. Inclusion of adults already diagnosed with diabetes might complicate the interpretation of the data; that is, as a consequence of the patho-physiology associated with diabetes, the response to exercise training with or without Dapagliflozin may differ in adults with diabetes compared with adults who are diabetes free.

c) If applicable, state the rationale for involvement of potentially vulnerable subjects to be entered into the study, including minors, pregnant women, economically and educationally disadvantaged, or decisionally impaired subjects. Specify the measures being taken to minimize the risks and the chance of harm to the potentially vulnerable subjects.

Potentially vulnerable subjects will not be studied.

d) If women, minorities, or minors are not included, a clear compelling rationale must be provided. Examples for not including minors: disease does not occur in children; drug or device would interfere with normal growth and development; etc.

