Clinical Research Protocol Title: Dapagliflozin Augments The Favorable Adaptation To Endurance Exercise Training

Protocol Type: Biomedical

Date Submitted: 11/01/2018

Approval Period: 11/06/2018-11/05/2019

Important Note: This Print View may not reflect all comments and contingencies for approval. Please check the comments section of the online protocol.
Questions that appear to not have been answered may not have been required for this submission.
Please see the system application for more details.

11/29/2017	CONTINUING REVIEW 3 FORM APPROVED	Y	Y
11/01/2018	CONTINUING REVIEW 4 FORM CREATED		
11/01/2018	CONTINUING REVIEW 4 FORM SUBMITTED	Y	
11/06/2018	CONTINUING REVIEW 4 FORM APPROVED	Y	Y

Methods of statistical analyses

Two-way analysis of variance (before training *vs.* after training, and Dapagliflozin *vs.* Placebo) with repeated measures on one factor (before *vs.* after) are used to examine differences in primary outcomes resulting from exercise training and/or drug treatment. Multiple comparisons of factor means will be performed using the Newman-Keuls test.

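### The planned ANOVA tests the drug through change scores; ANCOVA on the baseline already collected is usually more precise, and at worst slightly less so

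*Combined protocol and SAP*

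**What the plan says.** The whole analysis plan is the short paragraph headed Methods of statistical analyses, after the Event History. It specifies a two-way ANOVA, before versus after training and dapagliflozin versus placebo, "with repeated measures on one factor", namely before/after. These analyses "are used to examine differences in primary outcomes resulting from exercise training and/or drug treatment", followed by Newman-Keuls comparisons of factor means. It does not say which term is the test of the drug, and it names no covariate.

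The aim is in Purpose of the study, item 1b: "We wish to learn if Dapagliflozin augments the favorable adaptation to endurance exercise training in previously sedentary overweight/obese adult humans". The Overview under Study Procedures states that "Prior to and following completion of the treatment the following dependent variables will be quantified", so every outcome has a baseline value. Section 8a plans for 30 completers.

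Two assessments give several readings per visit. In the standardised exercise test, "Participants will exercise for 3 consecutive 10-minute periods at an external work rate of 25, 50 and 100 Watts". In the glucose tolerance test, blood "will be sampled at time 0 (baseline) and 5, 10, 15, 20, 30, 45, 60, 75, 90 105 and 120 minutes".

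**The concern.** In a two-way ANOVA of this kind, the term that asks whether the drug changes the response to training is drug-by-time. The drug main effect averages the before and after values. Randomised arms have the same expected baseline, so an effect of size d after training appears as (0 + d)/2 = d/2 in the main effect.

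With two time points, the drug-by-time test subtracts the whole baseline value from the post-training value. That is efficient only when the slope of post on baseline is near 1. If the slope is lower, subtracting the full baseline adds noise. The plan collects the baseline for every outcome but gives the analysis no means of estimating the slope. With about 30 completers, that lost precision matters.

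The issue is efficiency. The planned test is not biased.

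**Working it through.** **Inputs from the documents.** Two randomised arms; one assessment before and one after treatment; 30 planned completers. No alpha, power, effect size, SD or pre-post correlation is given, so there is no sample-size figure to reproduce.

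**Assumptions.** Equal arms (15 per arm, with 12 per arm as a smaller case), two-sided 5%, normal data, pre-post correlation rho = 0.5, 0.7, 0.8 or 0.9, and after/before SD ratio k = 0.9, 1.0 or 1.1. The baseline SD is set to 1.

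**Step 1: equivalence.** With two arms, two times and complete data, the interaction F equals t² on change scores, with N − 2 degrees of freedom. On simulated data sets:
- 15:15: F = t² = 0.3579, p = 0.554 for both tests
- 17:13: F = t² = 1.5799
- 14:12: F = t² = 0.2158

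**Step 2: variances per arm.** Let b = rho × k be the slope of post on baseline.
- Change score: 1 + k² − 2·rho·k = k²(1 − rho²) + (1 − b)²
- ANCOVA: k²(1 − rho²) × [1 + 1/(N − 4)]. The bracket is the expected cost of estimating the slope: 1 + 1/26 = 1.038 at N = 30, and 1 + 1/20 = 1.050 at N = 24.

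ANCOVA is therefore more precise when (1 − b)² > k²(1 − rho²)/(N − 4).

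**Step 3: worked cells at N = 30.**
- k = 0.9, rho = 0.5: change score 1 + 0.81 − 0.90 = 0.91; ANCOVA 0.81 × 0.75 × 1.038 = 0.631; ratio 1.442, a gain of 44%.
- k = 1.0, rho = 0.7: 0.60 against 0.51 × 1.038 = 0.530; ratio 1.133, a gain of 13%.
- k = 1.1, rho = 0.9: 1 + 1.21 − 1.98 = 0.23 against 1.21 × 0.19 × 1.038 = 0.239; ratio 0.963, a loss of 3.7%.

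**Step 4: participant-equivalent gain of ANCOVA (ratio − 1).**

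| N | k | rho 0.5 | 0.7 | 0.8 | 0.9 |
|---|---|---|---|---|---|
| 30 | 0.9 | 44.2% | 28.2% | 22.2% | 18.9% |
| 30 | 1.0 | 28.4% | 13.3% | 7.0% | 1.4% |
| 30 | 1.1 | 17.8% | 4.6% | −0.5% | −3.7% |
| 24 | 0.9 | 42.7% | 26.8% | 20.8% | 17.6% |
| 24 | 1.0 | 27.0% | 12.0% | 5.8% | 0.3% |
| 24 | 1.1 | 16.5% | 3.4% | −1.6% | −4.7% |

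**Step 5: the floor.** The loss is greatest when b = 1: 1/1.038 − 1 = −3.7% at N = 30 and 1/1.050 − 1 = −4.8% at N = 24. With equal SDs, break-even at N = 30 is rho = 0.926.

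**Step 6: detectable difference at 80% power, in baseline SDs, 15 per arm (change score / ANCOVA).** From the noncentral t with 28 and 27 degrees of freedom.

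| k | rho 0.5 | 0.7 | 0.8 | 0.9 |
|---|---|---|---|---|
| 0.9 | 1.01 / 0.84 | 0.79 / 0.70 | 0.65 / 0.58 | 0.46 / 0.42 |
| 1.0 | 1.06 / 0.94 | 0.82 / 0.77 | 0.67 / 0.65 | 0.474 / 0.471 |
| 1.1 | 1.12 / 1.03 | 0.87 / 0.85 | 0.711 / 0.714 | 0.51 / 0.52 |

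**Step 7: simulation.** With 200,000 trials per setting at 15 per arm, the simulated variance gains matched the formula to within 0.6 percentage points. At k = 1.0, rho = 0.5 and a true difference of 0.8 baseline SD, power was 56% for drug-by-time and 67% for ANCOVA. In the least favourable cell (k = 1.1, rho = 0.9, difference 0.45 SD) it was 70% and 68%.

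**The case against.** The strongest reply is that nothing here is wrong. The planned analysis is conventional and valid, and the documents cannot show that any particular outcome would gain. The 44% is one corner of an assumed grid. At correlations of 0.8 to 0.9 with SD ratios of 1.0 to 1.1, the effect is +7% to −4%. All of this stands. It makes the point an efficiency recommendation with an unknown gain for each outcome. It does not remove the asymmetry between a small bounded loss and a much larger possible gain.

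The plan never names drug-by-time as the drug test. That is also true. But the term belongs to the ANOVA described and is the only one that answers the stated aim, and leaving it unnamed is itself a reason to add a sentence.

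Timing is a real limit. In the continuing review, "Are you only performing data analysis" is answered yes and further recruitment is answered no. Participants were to learn their allocation at study completion. The documents do not say whether unblinded results have been seen. If they have, ANCOVA cannot become the planned analysis.

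Two sponsor-protocol attachments are listed but not supplied and may hold more statistical text, so this point concerns only the plan as supplied.

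The equivalence needs one value per visit. The workload and glucose-tolerance outcomes need a summary value first, and that choice is substantive: a mean over workloads could hide an effect at one workload.

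Finally, the 3.7% and 4.8% floors are on variance alone. Counting the lost degree of freedom at 80% power, the losses at rho = 0.9 and k = 1.1 are 3.9% at N = 30 and 5.1% at N = 24, which does not change the conclusion.

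**Conclusion.** The point holds as a recommended efficiency improvement. For an outcome with one value per visit, the term of the planned ANOVA that addresses the aim is a change-score t-test. ANCOVA on the collected baseline is more precise unless the slope of post on baseline is close to 1. At 15 per arm, over the assumed correlations and SD ratios, the effect runs from a 44% participant-equivalent gain to a loss of about 4%. It is negligible or slightly negative for outcomes with equal SDs and correlations above about 0.9. Confidence is medium, because the correlations, SD ratios, allocation and number analysed are all assumptions.

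**What to change.** - For the dapagliflozin-versus-placebo comparison of each outcome, specify ANCOVA of the post-training value on randomised arm and baseline value, and report the adjusted difference with a 95% confidence interval.
- Where a visit gives several readings, first name one summary value per visit. Examples are the mean over the three workloads and the 0–120 minute area under the curve.
- Keep drug-by-time as a sensitivity analysis, and keep the before/after analysis for the training effect.
- State in one clause that the drug main effect is not the test of the drug.
- Date the change before unblinded results are seen. If they have been seen, report drug-by-time as the planned test and label the ANCOVA post hoc.

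**Cost.** Three or four sentences of analysis wording, plus the choice of a summary value for the multi-reading outcomes. No new data are needed. ANCOVA uses one residual degree of freedom and adds about 4% expected variance at 15 per arm (5% at 12 per arm), which is a net loss only where the slope is close to 1.

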Document Name	SGLT2 Inhibitors Diabetes
Document Type	Other Protocol Material
Attachment	SGLT2 Inhibitors New Diabetes Drug
Document Name	SGLT2 Inhibitors New Diabetes Drug
Document Type	SOP
Attachment	HP-03-R1 Reporting AEs SOP
Document Name	HP-03-R1 Reporting AEs SOP
Document Type	Recruitment Material (e.g., flyers, email text, verbal scripts)
Attachment	14-5529H Recruitment Examples 02062015
Document Name	14-5529H Recruitment Examples 02062015
Document Type	Other Protocol Material
Attachment	Id cards for subjects
Document Name	Id cards for subjects
Document Type	Sponsor's Protocol
Attachment	Protocol ISSDAP0010-02062015
Document Name	Protocol ISSDAP0010-02062015
Document Type	Other Protocol Material
Attachment	FDA-1572_508(7.13)_05June2015
Document Name	FDA-1572_508(7.13)_05June2015

Protocol Title: Does Dapagliflozin Augment The Favorable Adaptation To Endurance Exercise Training?
Clinical Research Protocol Title: Dapagliflozin Augments The Favorable Adaptation To Endurance Exercise Training

Protocol Type: Biomedical

Date Submitted: 11/01/2018

Approval Period: 11/06/2018-11/05/2019

Important Note: This Print View may not reflect all comments and contingencies for approval. Please check the comments section of the online protocol.
Questions that appear to not have been answered may not have been required for this submission.
Please see the system application for more details.

Document Type**Sponsor's Protocol****Attachment**

[name] 0010 IISR FINAL

Document Name

[name] 0010 IISR FINAL

Document Type**Other Protocol Material****Attachment**

Important Communication from AZ regarding DKA other T2D studies 3 July 2015

Document Name

Important Communication from AZ regarding DKA other T2D studies 3 July 2015

Document Type**Other Protocol Material****Attachment**

AZ Email 07072015

Document Name

AZ Email 07072015

Document Type**Questionnaire/Survey****Attachment**

Screening Med History 08262015

Document Name

Screening Med History 08262015

Document Type**Other Protocol Material****Attachment**

FDA safety warning 04Dec2015

Document Name

FDA safety warning 04Dec2015

Document Type**Other Protocol Material****Attachment**

CDC Hepatitis B Fact Sheet

Document Name

CDC Hepatitis B Fact Sheet

Document Type**Recruitment Material (e.g., flyers, email text, verbal scripts)****Attachment**

Recruitment_AZ_Exercise

Document Name

Recruitment_AZ_Exercise

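### The augmentation question is not tied to the drug-by-time contrast, and adjusting for the before-training value would test it more efficiently than the planned ANOVA

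*Combined protocol and SAP*

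**What the plan says.** The aim is in Purpose of the study, item 1b: "We wish to learn if Dapagliflozin augments the favorable adaptation to endurance exercise training in previously sedentary overweight/obese adult humans". Both arms train. The Overview under Study Procedures says "30 sedentary adults will be recruited for participation and randomly assigned to one of two 12-week treatments", and the outcomes are measured on both sides of treatment: "Prior to and following completion of the treatment the following dependent variables will be quantified". Subject Population, item 8a, gives the target number of completers: "We plan to complete the study in 30 overweight/obese adult volunteers (men and women".

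The statistical text is two sentences under Methods of statistical analyses, at the end of the document after the Event History. The first names a two-way analysis of variance with time (repeated) and drug as factors; these analyses "are used to examine differences in primary outcomes resulting from exercise training and/or drug treatment". The second is "Multiple comparisons of factor means will be performed using the Newman-Keuls test".

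Neither sentence names the interaction, a difference in change, an estimate with its interval, or a rule for concluding augmentation. The supplied text also gives no significance level, SD, expected gain or before-after correlation.

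**The concern.** Both arms receive the same training, so augmentation can only mean that the change is larger on drug than on placebo. The planned model yields several tests: time, drug, drug by time, and pairwise comparisons of means. Only drug by time is the difference in change. The time effect and the within-arm before/after comparisons show that training works, not that the drug adds to it. The drug main effect is a valid randomised comparison, but it averages before and after values and so halves the drug effect.

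Two things are at stake. First, the text leaves open which result carries the conclusion, and some candidates have different error rates. Second, even the right contrast in the planned model uses the before-training value by plain subtraction. When the before-after correlation is low or moderate, subtraction adds noise, which costs power in a trial of about 30 completers.

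**Working it through.** **Inputs.** From the documents: 30 participants, two arms, one measurement before and one after. Assumed, because the documents do not say: equal split (n = 15 per arm), SD σ = 1 at each time, correlation ρ from 0.3 to 0.9, two-sided 5%, normal data, drug effect δ = 0.6 SD for power. The plan states no power or effect size, so there is no planned figure to reproduce.

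**1. The planned model holds a valid test.** In a 2×2 mixed ANOVA the interaction F equals the squared two-sample t on change scores. A numerical check on simulated data gave 2.4038 for both.

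**2. Efficiency.** Per-participant variance is 2σ²(1−ρ) for the change score and σ²(1−ρ²) for ANCOVA. The ratio is (1−ρ²) / [2(1−ρ)] = (1+ρ)/2, before the small loss of one degree of freedom.

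**3. Power at δ = 0.6.** For the interaction, the noncentrality is [0.6 / √(2(1−ρ))] × √(15/2) on 28 df. ANCOVA (27 df) was simulated with 40,000 trials per setting.

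| ρ | SD of change | Noncentrality | Interaction power | ANCOVA power | Variance ratio (1+ρ)/2 |
|---|---|---|---|---|---|
| 0.3 | 1.183 | 1.389 | 27% | 37% | 0.65 |
| 0.5 | 1.000 | 1.643 | 35% | 44% | 0.75 |
| 0.8 | 0.632 | 2.598 | 71% | 74% | 0.90 |
| 0.9 | 0.447 | 3.674 | 94% | 94% | 0.95 |

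The drug main effect has 17%, 15% and 13% power at ρ = 0.3, 0.5 and 0.8.

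**4. What Newman-Keuls could be comparing.** Each factor has two levels, so comparing marginal means adds nothing to the F tests. Multiple comparisons remain only among the four arm-by-time means, giving six pairs, of which two are within-arm before/after pairs. That the test covers these pairs is an inference from the design; the text does not state it.

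**5. Illustration with no drug effect.** Step-down Newman-Keuls on 28 df, 40,000 trials per setting. Between-arm pairs use an error term that includes between-subject variation. The table gives the rate of significance in the drug arm only.

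| Training gain (SD) | ρ = 0.5 | ρ = 0.8 |
|---|---|---|
| 0.3 | 5% | 6% |
| 0.5 | 13% | 11% |
| 0.7 | 18% | 11% |
| 0.8 | 18% | 9% |
| 1.0 | 11% | 4% |
| 1.5 or more | 0.3% or less | 0.3% or less |

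The benchmark is 2.5%, the rate at which the interaction or ANCOVA falsely favours the drug. If a significant interaction is required first, the drug-arm-only rate is about 1.4% to 2.4% at gains of 0.3 to 0.8 SD.

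**6. Error term.** A false post-training difference between arms, counted in either direction and so set against 5%, occurs in 2% to 5% of trials with between-subject error (gains 0.5 to 3 SD). With within-subject error for all pairs it occurs in 12% to 37%.

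**The case against.** The strongest reply is that the plan already contains the right test and never says otherwise. A mixed ANOVA is normally read through its interaction, and pairwise comparisons usually follow a significant one. Under that reading the drug-arm-only rate is below the nominal 2.5%, so nothing is inflated. All of this stands. A reader might infer that the plan will treat a significant change in the drug arm alone as augmentation, with a false-positive rate of 9% to 18%. The documents do not support that: no sentence makes within-arm results decisive, and the rate depends on a gain, SD and correlation that are nowhere given. Nor does the planned analysis ignore the baseline, since the interaction subtracts it.

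The preference for ANCOVA can also be challenged. Its gain is about 3 points at ρ = 0.8 and nil at 0.9. A switch at the analysis stage is itself a late choice, and the continuing review form answers yes to "Y Are you only performing data analysis". That limits how ANCOVA may be used if the arms have been compared, but it does not remove the efficiency gain at lower correlations.

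Finally, the Attachments list includes "Protocol ISSDAP0010-02062015" and a second sponsor protocol, neither supplied. The reference list holds a paper on power for repeated-measures models that the supplied text does not cite, so a fuller statistical section may exist.

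**Conclusion.** The concern holds in a limited form. The planned ANOVA is suitable and includes a valid test of augmentation. The supplied text does not designate that test, and it leaves the Newman-Keuls comparisons without a precondition or error term. A better method is available from data the trial already collects: ANCOVA has (1+ρ)/2 of the change-score variance. Under the stated assumptions that raises power for a 0.6 SD effect by about 10, 9 and 3 percentage points at correlations of 0.3, 0.5 and 0.8, with no material gain at 0.9.

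The Newman-Keuls rates illustrate why the decisive contrast and the error term should be written down. They do not estimate this trial's error rate. The point should be fixed before results are reported, but it does not invalidate the design. Confidence is medium, because the documents give no SD, gain, correlation or allocation ratio, and the sponsor protocols may already name the contrast.

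**What to change.** For each primary outcome, estimate the between-arm difference in the after-training value adjusted for the before-training value, tested two-sided at 5% with a 95% confidence interval. Report the planned drug-by-time interaction beside it. If the arms have already been compared, keep the interaction as the planned test and label ANCOVA as a later, supportive analysis.

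Drop Newman-Keuls or keep it as description only, with an error term that includes between-subject variation for between-arm pairs. State that within-arm p-values are not evidence of augmentation. If a sponsor protocol already names the contrast, cite it.

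The cost is a few sentences and one degree of freedom; no new data are needed. ANCOVA carries less weight if adopted after unblinding. Multiplicity across the several outcome domains needs its own rule, which this change does not supply.
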